- 2.3 Nearly four percent of the global population has KOA, with the global female percentage nearing five percent. Additionally, the years lived with disability (YLDs) resulting from the disorder increased by 64.8% from 1990 to 2010.⁸ The picture is not much better in the United States, where osteoarthritis ranks eighth highest in YLDs compared to other pathologies.⁹ The rate of KOA has continued to climb here in the U.S., doubling in the past half-century even when accounting for increased life expectancy and higher average BMI,¹⁰ both of which are considered risk factors in the development of KOA.¹¹

Patients with KOA have been shown to have gait abnormalities when compared to healthy controls, including alterations in trunk and pelvic kinematics,¹² lower extremity kinematics^{13,14} and kinetics,¹⁴⁻¹⁸ gait speed,^{13-17,19} and functional outcome measure scores.¹⁹ Some of these differences, like an increased external knee adduction moment (KAM)^{20,21} and a decreased peak stance knee

PROTOCOL TITLE: The Effects of Core Activation and Stabilization Training on Gait Kinetics, Kinematics, and Speed, and Self-Perceived Function in Patients with Knee Osteoarthritis

flexion angle (KFA),¹⁴ have been shown to correlate with the advancement of KOA and may be causative in nature. Others, like an increased T₁¹⁶ and reduced freely chosen gait speed,²² may be compensatory.²³ The same has been found in regard to the reduced second peak ground reaction force in the sagittal plane (F₂) observed in this population.¹⁸

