3.0 Inclusion and Exclusion Criteria*

- 3.1 Potential participants will be screened for eligibility by the PI once they have expressed interest either by contacting the PI themselves, or upon being referred by someone familiar with the investigation. Assurance of meeting the inclusion and exclusion criteria will be ensured during the informed consent process.
- 3.2 The inclusion and exclusion criteria for this investigation are as follows:

Inclusion criteria:

English-speaking men and women, 40 years old and older, of any race or ethnic group, with a documented diagnosis from a medical provider (i.e., physician, physician assistant, or nurse practitioner, etc.) of KOA, unilaterally or bilaterally. Previous or current physical therapy patients may be included (see exclusion criteria for exceptions). *Healthy controls* will meet the same requirements, but without a medical diagnosis of KOA and have the ability to ambulate on a level surface without any report of pain in their knees at the time of gait assessment.

PROTOCOL TITLE: The Effects of Core Activation and Stabilization Training on Gait Kinetics, Kinematics, and Speed, and Self-Perceived Function in Patients with Knee Osteoarthritis

Exclusion criteria: those with other lower extremity injuries (orthopaedic, cardiovascular, neurologic, etc.) which are currently hindering their ability to ambulate, those with current complaints of low back pain, those who have undergone bilateral total knee arthroplasty, those with concomitant diagnosis of rheumatoid arthritis, those persons not able to ambulate independently with or without an assistive device, those who have received a corticosteroid injection within the past two months, those who have received a hyaluronic acid injection in the past six months, and those persons currently enrolled in a core training program as part of formal physical therapy or physical fitness.

3.3 Special populations will not be included in this investigation for the following reasons:

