9.0 Procedures Involved*

9.1 This investigation will be divided into three parts, each associated with one of the specific aims detailed in Section 1. All procedures will be performed in the School of Allied Health Professions, either in the Motion Analysis Laboratory (Gait Lab) or the Rehabilitation Faculty Practice (RFP) Clinic.

Part 1: Compare age and gender matched healthy controls and KOA groups on kinetics, kinematics, and gait speed during self-selected speed via a between groups analysis across the dependent variables, and determine if those differences in the KOA group have a predictive relationship with their KOOS scores.

Part 2: Within-group comparison of both groups (with and without volitional TA activation) and between-groups (control group versus KOA group). Compare pain levels during both conditions via NPRS for the KOA group. Participants will wear biofeedback under both conditions, and all condition trials will be randomized. Alarm or verbal cue will be provided at 30% MVIC, and two electrodes placed over TA/obliquus internus (OI) just medial to anterior superior iliac spine (ASIS). A comparison of TA activation will be performed both within and between groups.

Part 3: Within-groups comparison of KOA group (pre-treatment and post-treatment; six-week training program) on kinetics, kinematics,

PROTOCOL TITLE: The Effects of Core Activation and Stabilization Training on Gait Kinetics, Kinematics, and Speed, and Self-Perceived Function in Patients with Knee Osteoarthritis

and gait speed during self-selected paced ambulation. A comparison of KOOS scores before and after treatment will be performed as well.

9.2 Once recruitment (see 22.0) and informed consent (see 27.0 and 28.0) are completed:

Part 1: All participants will undergo anthropometric data collection first, including weight, height, leg length, knee joint width, and ankle joint width. Age matching will be done within +/- 5 years between the two groups. Reflective markers will then be placed on bilateral lower extremities following the Plug in Gait Model. EMG electrodes will be placed bilaterally just medial to the ASIS, over the TA/OI. The Gait Lab will undergo calibration, and the participant will undergo a static trial. In participants with bilateral KOA, the most painful limb, identified by subjective report, will be used in the data collection procedures. Healthy controls will undergo analysis of their dominant limb by indicating with which leg they would kick a ball.

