11.0 Data Management* and Confidentiality

- 11.1 Data analysis will be performed by the PI, with the assistance of the sub-investigator. The PI will use the latest version of SPSS available to the PI on his personal laptop computer (see 11.3 for security details). The kinetic, kinematic, and speed data will be analyzed together, either by a MANOVA (if assumptions are met) or separate ANOVA/mean comparison analyses with Bonferroni corrections, while the pain NPRS and KOOS scores will be analyzed each individually via means comparisons. The EMG data will be analyzed via a 2x2 ANOVA or separate means comparisons. If the groups have significantly different mean BMIs, then it will be included in the kinetic and kinematic analysis as a covariate. The predictive relationship between the number of exercise sessions and the change observed within the KOA group for each variable will be analyzed via regression analysis.
- 11.2 An *a priori* power analysis was performed to determine the number of participants required to achieve significance for the variables of highest interest in the investigation. Data from previous publications on these variables were used in the power analysis. These include the following: T₁ between¹⁶ and within ([name], [name], unpublished data, May 2018) groups, F₂ between and within groups,¹⁸ KAM between and within groups,¹⁷ KFA between¹⁴ and within²⁶ groups, and gait speed between¹⁶ and within²⁷ groups for the kinetic and kinematic analyses. Additionally, the KOOS²⁸ was examined for within-group means comparison. The PI used G*Power (Heinrich-Heine-University Düsseldorf, Düsseldorf, Germany) for the purposes of these analyses. It was determined that 45 participants would be required, except for the KFA which would require a larger sample size. Since this variable will be collected concurrently along with the other kinetic and kinematic data, and all the other variables of interest are appropriately powered at a much lower sample size, we felt confident proceeding regardless of being underpowered for one of these five dependent kinetic/kinematic variables of interest.

Since this study involves a six-week intervention, an attrition rate of 10% was assumed, so a total of 50 participants (25 healthy controls and 25 with KOA) will be recruited. Data analysis will be completed

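### BMI is adjusted for in the KOA-versus-control gait comparison only if a significance test finds a BMI difference, so modest imbalance stays in the contrast

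*Combined protocol and SAP*

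**What the plan says.** Section 11.1 sets the rule: "If the groups have significantly different mean BMIs, then it will be included in the kinetic and kinematic analysis as a covariate". Neither the alpha nor the form of the BMI test (paired or unpaired) is given, and no other section adjusts for BMI.

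The surrounding design does not control BMI:

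- **Matching (9.1, Part 1)** uses age and gender only: "Compare age and gender matched healthy controls and KOA groups on kinetics, kinematics, and gait speed during self-selected speed".
- **Eligibility (3.2)** sets no BMI limit; it admits "English-speaking men and women, 40 years old and older, of any race or ethnic group".
- **Background (2.3)** says of longer life expectancy and higher average BMI: "both of which are considered risk factors in the development of KOA".

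The data for adjustment will exist (9.2, Part 1): "All participants will undergo anthropometric data collection first, including weight, height, leg length, knee joint width, and ankle joint width".

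The gait variables go into a MANOVA if its assumptions hold, and otherwise into "separate ANOVA/mean comparison analyses with Bonferroni corrections" (11.1). Section 11.2 counts "five dependent kinetic/kinematic variables of interest", of which speed is one. Planned recruitment is 25 KOA participants and 25 controls.

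**The concern.** In a non-randomised comparison, the bias from leaving out BMI is the BMI gap multiplied by the BMI-outcome slope. The p-value of the gap measures neither; at 25 per group it largely reflects the sample size. A rule driven by that p-value leaves small and moderate gaps in place. It also lets the data choose which model is reported.

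What is exposed is the Aim 1 group contrast and the main between-group contrast in Aim 2. Two features of the plan add to this. Aim 1 H2 carries forward the gait variables that differ significantly between groups as KOOS predictors, so the group contrast influences what is analysed next. Section 11.2 also plans repeated analyses with early stopping of recruitment. The BMI test is weaker at smaller numbers, so the model could switch between looks.

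The within-person comparisons (Aim 2 within group, Aim 3 pre to post) are not affected. A BMI effect that is the same with and without core activation also cancels from the group-by-condition interaction.

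**Working it through.** **Plan's own figure.** Section 11.2 requires 45 participants and assumes 10% attrition: 45 / (1 − 0.10) = 50, or 25 per group. This reproduces. The 45 itself cannot be checked, because its effect sizes, SDs, alpha and power are not given.

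**Assumed inputs, not in the documents.** BMI test at two-sided 0.05, unpaired; true BMI gap g of 0.3, 0.5 or 0.8 within-group SD; BMI-outcome correlation r of 0, 0.1, 0.3 or 0.5; no true group effect; one analysis at 25 v 25.

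**Step 1: smallest observed gap that triggers adjustment.** Threshold = t(1 − α/2, 48 df) × √(2/25).

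| BMI test | Threshold (SD) |
|---|---|
| Unpaired, α 0.05 | 2.0106 × 0.2828 = 0.569 |
| Unpaired, α 0.10 | 1.6772 × 0.2828 = 0.474 |
| Unpaired, α 0.01 | 2.6822 × 0.2828 = 0.759 |
| Paired, α 0.05, 24 df, within-pair correlation 0 | 0.584 |
| Paired, α 0.05, 24 df, within-pair correlation 0.3 | 0.488 |

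With 45 participants (23 v 22) the unpaired 0.05 threshold rises to 0.601.

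**Step 2: chance that the rule adjusts** (noncentral t, 48 df, noncentrality g × √12.5): 18% at g = 0.3, 41% at 0.5 and 79% at 0.8.

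**Step 3: bias.** Average bias = r × E[observed gap × 1(BMI test not significant)], by numerical integration. The observed gap is N(g, 2/25) and the pooled variance is chi-square(48)/48.

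| r | Average bias, g = 0.3 / 0.5 / 0.8 | Bias among studies left unadjusted |
|---|---|---|
| 0.1 | 0.018 / 0.019 / 0.009 | 0.021 / 0.032 / 0.042 |
| 0.3 | 0.052 / 0.056 / 0.026 | 0.064 / 0.095 / 0.126 |
| 0.5 | 0.087 / 0.094 / 0.044 | 0.107 / 0.159 / 0.209 |

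Units are outcome SD. At r = 0 the bias is nil. The standard error of the unadjusted contrast is √(2/25) = 0.283 SD. Over r 0.3 to 0.5, average bias is 0.01 to 0.06 if the BMI test uses α 0.10, and 0.07 to 0.16 if it uses 0.01.

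**Step 4: error rates and precision.** Monte Carlo, 200,000 replicates per cell; outcome = r × BMI + error, with unit within-group variance; ANCOVA (47 df) against t-test (48 df).

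- Type I error under the rule, r 0.3 to 0.5: 5.1 to 6.0% at the 5% level, and 1.0 to 1.2% at the 1% level (0.05/5). If the BMI test uses 0.01, it is 1.3 to 2.1% at the 1% level (100,000 replicates).
- Family-wise error over five Bonferroni-tested variables (60,000 replicates, assumed residual correlation 0.3): 4.6 to 5.4% under the rule, 4.6 to 4.8% if BMI is always included.
- RMSE, r 0.3 to 0.5: 0.284 to 0.300 under the rule, 0.250 to 0.295 if always adjusted. At g = 0.5, r = 0.5 it is 0.290 v 0.256.
- RMSE, r = 0: 0.286 to 0.308 under the rule, 0.289 to 0.310 if always adjusted, a cost of at most about 0.003.

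**The case against.** The strongest case on the other side is about weight.

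- **The effect is small and rests on assumed inputs.** Average bias of 0.03 to 0.09 SD is well under the standard error, and false positives hardly move. At r = 0.1 the existing rule is marginally better on RMSE (0.287 v 0.288, 0.293 v 0.294 and 0.306 v 0.307 at gaps 0.3, 0.5 and 0.8). At r = 0.3 the gain from always adjusting is only about 0.005 to 0.010; it becomes clear only near r = 0.5. One r is applied to five different variables, and the documents do not say whether F2 and KAM are scaled to body mass. All of this stands. It makes the point a cheap improvement, but it does not justify a p-value as the trigger.
- **The rule already handles the worst cases.** It is written in advance, names one covariate, and adjusts in 79% of studies at a true gap of 0.8 SD. That is so, but it misses most studies with gaps of 0.3 to 0.5 SD.
- **Aim 1 may intend a plain comparison of two populations,** in which a BMI difference is part of how they differ. That is a legitimate question, and reporting the unadjusted contrast answers it. But the plan itself adjusts once the gap is significant, so under the present rule the question being answered changes with a p-value.
- **The error rates are for the separate-test fallback at a single look,** not for the MANOVA or for repeated looks. This limit stands. The bias in Step 3 concerns each variable's contrast and does not depend on the MANOVA, but it too assumes one analysis at 25 v 25.

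**Conclusion.** The concern holds. Followed as written, the rule leaves modest confounding by body size in the KOA-versus-control contrasts and makes the reported model depend on the data. With an unpaired two-sided 0.05 test at 25 per group, observed gaps below about 0.57 SD are not adjusted for. For assumed gaps of 0.3 to 0.8 SD and correlations of 0.3 to 0.5, the bias averages 0.03 to 0.09 outcome SD, and 0.06 to 0.21 SD among the studies left unadjusted.

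False-positive inflation is near nil at the Bonferroni level if the BMI test uses 0.05. The case therefore rests on bias, precision and pre-specification. The change should be made, but the study as a whole is not threatened. Confidence in the size is moderate, because the gap, the correlation, the alpha and the form of the test are all assumptions.

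**What to change.** Replace the conditional sentence in 11.1 with:

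> All KOA-versus-control analyses of the gait variables, including speed, will include BMI as a covariate regardless of the observed BMI difference; the unadjusted matched contrast will also be reported.

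Add that significance is decided from the BMI-adjusted model, so that reporting both contrasts does not reopen the choice. Naming speed only clarifies, since 11.2 already counts it among the five variables.

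The cost is one sentence and no new data, because height and weight are measured in everyone. Statistically it costs one degree of freedom (47 instead of 48). The interval widens somewhat if the BMI gap is large and BMI is weakly related to the outcome. Compared with no adjustment, the variance ratio is 1.09 at gap 0.8, r 0.3 (SE 0.295 v 0.283 SD) and 1.19 at gap 0.8, r 0 (SE 0.310 v 0.283 SD). At a gap of that size the present rule would itself adjust in 79% of studies.

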7.0 Study Timelines*

7.1 Each participant with KOA will actively participate in the study eight weeks, depending on the participants scheduling abilities. This will require 10-12 hours total of participation. Participants in the control group are the exception, as they will only be required to attend one session for full participation. This single session will last about 1-2 hours. It is anticipated that it will take approximately 12-18 months to enroll all study participants, with completion of data collection/analyses within this same timeline.

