8.0 Study Endpoints*

8.1 The primary endpoint of this investigation will be the completion of all data collection, with all participants in both the control and experimental groups having concluded their participation.

The secondary endpoint will be the completion of all data analysis, and preparation for dissemination of the research findings.

8.2 NA.

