PROTOCOL TITLE: The Effects of Core Activation and Stabilization Training on Gait Kinetics, Kinematics, and Speed, and Self-Perceived Function in Patients with Knee Osteoarthritis

intermittently throughout data collection, and if significance is achieved prior to 50 participants completing their participation, recruitment will be discontinued, and only those in the study will be allowed to complete the study. This will be done in an effort to reduce the number of people undergoing this less than minimal risk investigation.

- 11.3 The kinetic and kinematic data will be stored on the computer system in the Gait Lab. This lab is key accessible by the faculty of the SAHP. The computer system is password protected, with the PI and the sub-investigator being the only two individuals who currently know that password. Other faculty members would need to get the password from these two investigators for their own research activities unrelated to this investigation. The data will be backed up on an external hard drive belonging to the two investigators. No personal identifying information will be included in this data, as the participants will be identified by their participant identification numbers. The key to these identifiers will be the signed consent forms maintained by the PI that have both the participants' names and identification number on them. These forms will be maintained in the PI's office (SAHP Rm 2-234) which is key access, in a compliance binder. The data collection forms and KOOS questionnaires will also be located in this binder, with only the identification number on them. All of the deidentified raw data, including kinetic, kinematic, gait speed, NPRS ratings, and KOOS scores will also be maintained on the PI's personal laptop and work desktop computers for the purposes of data analysis, and preparations for dissemination after the completion of the data collection and analysis. Both of these computers are password protected. This de-identified data will be backed-up on the PI's personal flash drives.

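### Recruitment may stop when significance is reached at unscheduled looks, with no trigger outcome named and no error control across looks

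*Combined protocol and SAP*

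**What the plan says.** Section 11.2 plans analysis "intermittently throughout data collection" and then states the rule: "if significance is achieved prior to 50 participants completing their participation, recruitment will be discontinued". People already enrolled carry on: "only those in the study will be allowed to complete the study". The reason given is to expose fewer people to a study it describes as below minimal risk.

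The only multiplicity provision is in 11.1. The gait variables are analysed "either by a MANOVA (if assumptions are met) or separate ANOVA/mean comparison analyses with Bonferroni corrections", while pain and the Knee Injury and Osteoarthritis Outcome Score (KOOS) are each compared separately with no correction stated.

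Section 11.2 refers to the variables of most interest (five gait variables between and within groups, plus KOOS) but designates none for stopping. Section 8.1 does not help: its primary endpoint is the end of data collection, "with all participants in both the control and experimental groups having concluded their participation", which is a milestone and not an outcome.

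On timing, section 7.1 says "It is anticipated that it will take approximately 12-18 months to enroll all study participants", with data collection and analysis finishing inside the same period. It adds "Each participant with KOA will actively participate in the study eight weeks", and says of controls that "they will only be required to attend one session for full participation".

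**The concern.** A test repeated on accumulating data, with recruitment ended when it first crosses the usual threshold, rejects a true null more often than its nominal level. It also tends to stop on a chance high, so the estimate is biased away from zero. P-values and confidence intervals computed as for a fixed sample do not allow for either effect.

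The unnamed trigger adds a second problem. All three aims share participants. If a between-group result (Aim 1) or a volitional-activation result (Aim 2) may end recruitment, the six-week training question (Aim 3) can be cut short by a comparison unrelated to it. The plan also does not say whether a look uses first-visit data or only participants who have finished every part, and that decides how much data arrives after a stop.

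**Working it through.** **1. The plan's own figure.** 45 required with 10% attrition gives 45 / 0.90 = 50, or 25 per group, as stated. The 45 itself cannot be rebuilt, because alpha, power, effect sizes and SDs are not given. The sample size has no allowance for repeated looks that can be identified.

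**2. Participants in progress at a stop.** Inputs from 7.1: 25 KOA participants, eight weeks each, everything finished within 12-18 months (52-78 weeks). The last KOA enrolment must then fall at least eight weeks before the end. With even enrolment, number in progress = 25 / (T - 8) x 8.
- T = 52: 25 / 44 x 8 = 4.5
- T = 78: 25 / 70 x 8 = 2.9

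So about 3 to 4.5 KOA participants are still to finish. Controls attend once and add almost none. Outcomes taken at the first visit (Aims 1 and 2) also have little overrun.

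**3. False-positive rate for one designated outcome.** Assumed, because the plan is silent: two-sided 0.05 at every look, and looks at the per-group sizes shown. The quantity is P(p < 0.05 at any look) under the null. For the overrun columns, the test must also remain at p < 0.05 after the extra participants are added. Simulated t-tests, in per cent:

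| Looks (n per group) | Stop, between groups | Stop, paired | Between groups, 3-4 more KOA only | Paired, 3-4 more | Paired, 5 more |
|---|---|---|---|---|---|
| 2 (13, 25) | 8.4 | 8.5 | 6.7-6.9 | 6.1-6.4 | 5.8 |
| 3 (8, 17, 25) | 10.7 | 11.0 | 7.5-7.8 | 6.5-6.9 | 6.2 |
| 5 (5, 10, 15, 20, 25) | 14.3 | 15.1 | 8.8-9.3 | 7.2-7.9 | 6.6 |

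Repeat runs differ by at most about 0.4 points. A large-sample normal calculation with equally spaced looks gives 8.3, 10.7 and 14.2% at the stop for 2, 3 and 5 looks.

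**4. Bias.** For a true between-group difference of 0.5 SD, the average estimate at the stop is 0.55, 0.59 and 0.63 for 2, 3 and 5 looks, against 0.50 with one analysis.

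**5. Other triggers.**
- *Any of several outcomes.* Take five gait variables at 0.05 / 5 = 0.01 each plus KOOS at 0.05, correlation 0 to 0.5. The rate at the stop is about 15-16% with 2 looks and 25-29% with 5, and about 11-15% after 3 more participants. A single look already gives 8-9%, so part of this is multiplicity across outcomes and not across looks.
- *All five gait variables required.* If all five are null, the rate is 0.1% or less at 0.01 each and at most 1.2% at 0.05 each. If four truly differ and one is null (independent variables, 0.05 each, 2 to 5 looks), the null one is falsely declared in about 4-6% of trials when the others differ by 1.0 SD, and about 8-13% at 2.0 SD.

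**6. Aim 3, only if an Aim 1 result may trigger the stop.** Assumed: 10% attrition, a paired t-test, and power averaged over the simulated stopping sizes plus 3 more KOA participants. Full sample: 22 completers.
- Aim 3 effect 0.6 SD: 77% at full sample. It falls to 71, 69 and 66% for 2, 3 and 5 looks if the Aim 1 difference is 0.5 SD, and to 66, 61 and 57% if it is 0.8 SD.
- Aim 3 effect 0.8 SD, Aim 1 difference 0.5 SD: 95% falls to 91-85%.
- Aim 3 effect 1.0 SD, Aim 1 difference 0.5 SD: 99% falls to 98-94%.

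With 3 more KOA participants, mean KOA enrolment for 2, 3 and 5 looks is 22.9, 21.9 and 20.8 (Aim 1 difference 0.5 SD), or 20.5, 18.9 and 17.2 (0.8 SD), instead of 25.

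**The case against.** The strongest reply is that enrolled participants finish, so the reported test may come after overrun, and overrun pulls the rate back towards 5%. That stands in part. With five more participants, a paired Aim 3 outcome is at about 6-7%. But overrun reduces the excess without removing it, it barely applies to first-visit outcomes, and no section says which test is reported.

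A second reply is that every percentage above depends on inputs the plan does not give. That is correct, and the figures are illustrations. It does not answer the point that the rule has no determinate error rate.

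Third, a strict trigger such as all five gait variables might seem protective. It gives a very low rate only when all five are null, so it is not a general safeguard.

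Some stronger readings are tempting but not supported:
- A reader might infer an error rate of 25-29%. That needs any of several outcomes to trigger the stop, which the plan neither says nor excludes.
- A reader might infer that Aim 3 will be left underpowered. That needs an Aim 1 or 2 trigger, and the loss depends on an Aim 3 effect the documents do not give. The 45 is also a two-group total, not an Aim 3 requirement, and 11.2 says every variable except the knee flexion angle is adequately powered at a much smaller sample.
- A reader might take 8.1 to forbid testing before collection ends. It lists milestones and does not bar earlier tests.

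**Conclusion.** The point stands as a defect of the rule. Recruitment can end on an unspecified significant result at an unspecified number of looks, and nothing in the plan controls error across them. This is certain from the text.

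The size is conditional. For one designated outcome at two-sided 0.05 with 2 to 5 looks, the false-positive rate is about 8-15% at the stopping look or on first-visit data, and about 6-9% once the 3-4 KOA participants in progress are added. It is higher if any of several outcomes may trigger the stop. Estimates at the stop are inflated by roughly 10-26% for a true 0.5 SD (0.55 / 0.50 = 1.10; 0.63 / 0.50 = 1.26).

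The possible shortfall in Aim 3 is a further consequence only if Aim 1 or 2 may trigger the stop. With an Aim 1 difference of 0.5 SD and three more KOA participants finishing, the power loss is modest for an Aim 3 effect of 0.8 SD or more and larger at 0.6 SD. It grows if the Aim 1 difference is bigger, because stops then come sooner.

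The rule should be changed before any look is taken, because unplanned looks cannot be undone afterwards.

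**What to change.** Delete the early-stopping sentence in 11.2, recruit the planned 50, and state that the inferential tests are run once, after all enrolled participants have finished. This is a wording change with no participants beyond the plan. The only loss is the chance to stop early, and the very low risk that the protocol claims makes that chance worth little.

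If a look is kept:
- Make it a single interim at a pre-specified number of completers, on one pre-named Aim 3 outcome, so that a baseline comparison cannot end recruitment for the training question.
- Use an O'Brien-Fleming boundary, about p < 0.005 at the interim and p < 0.048 at the end. With paired t-tests at 11 and 22 completers the simulated overall error is 5.0-5.1%.
- State that, if recruitment stops, the interim crossing is the formal test of that outcome, and report the estimate with everyone enrolled included.
- State that a stop also shortens Aims 1 and 2, and that this is accepted.

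This fallback saves little. It would stop about 12% of trials at a true 0.6 SD and 26% at 0.8 SD.
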